#### 9.1.2 Guidelines for archival specimens

Using the formalin-fixed paraffin embedded (FFPE) tissue block, the following samples will be processed for correlative studies:

- If tissue block is available submit:
  - 6 paraffin scrolls measuring 10  $\mu$ m thick placed into a Nunc tube and frozen at -80° C AND
  - 10 x 5  $\mu$ m unstained slides
- If tissue block is unavailable submit 20 x 5  $\mu$ m unstained slides

#### 9.1.3 Guidelines for fresh tumor tissue processing

##### 9.1.3.1 *Non-COH sites*

Tumor lesion core or excisional biopsies should be flash frozen and kept at -80°C until batch shipment.

##### 9.1.3.2 *COH only*

Tumor lesion core or excisional biopsies will be collected in saline.

#### 9.1.4 Labeling of samples

Samples will labeled with the study number, institution (for non-COH sites), subject ID, date, timepoint of collection (i.e. baseline or progression) and if applicable patient initials.

**9.1.5 Sample shipment and receiving lab**

Tissue specimens collected at the above indicated timepoints will either be taken to (COH only) or batch-shipped (non-COH sites) to COH Pathology Core. For all sites, please include the **Correlative Tissue form (Appendix F-2)** with your shipment.

Please note that samples should only be **batch shipped from non-COH sites on Monday-Wednesday** for receipt Tuesday-Friday. Refer to [Appendix F-1](#) for shipment details.

## 10.0 STUDY CALENDAR

All procedures may increase in frequency if clinically indicated.

**Table 10.0 Study Activity Calendar**

Protocol Activity dd	Screening a	Protocol Therapy b,c							EOT g	Post-last Dose Follow-up (24 months)			
		Cycle 1					Cycle 2 D1 & then weekly	Cycle 3+ D1		Safety 30-days post h	Response i	Survival j	
		D 1 d,e	D 2-7 f	D 8	D 15	D 22							
Informed Consent k	X												
Medical History l	X												
Eligibility m	X												
Registration n	X												
Physical Exam o & Vital signs p	X	X	X	X	X	X	X	X	X	X	X		
Height	X												
ECOG Status (Appx. A)	X	X	X	X	X	X	X	X	X	X	X		
Con-med review q	X	X	X	X	X	X	X	X	X	X	X		
AE Assessment r	X r	-----X s -----											
12-lead EKG	X u												
Pregnancy t	X u												
CBC w/diff, plt & Serum chemistry v	X u	X	X f	X	X	X	X	X	X	X			
TLS serum chemistry monitoring w		X w	X w	X w									
CT/MRI imaging x	X							X y	X g		X		
FDG-PET scan z	X								X				
Bone marrow biopsy/ aspirate	X aa												
Response bb							X y	X			X		
TLS prophylaxis	X cc												
Venetoclax		Orally, daily e,f											
Romidepsin ee		X		X	X		X ee	X ee					
Pill diary ff		X	X	X	X	X	X	X	X				
Tumor tissue	X gg	Optional: During Cycle 1 or 2 hh											
Survival status j												X	

- a. Screening activities to occur within 28 days prior to start of protocol therapy except for [laboratory assessments](#), [bone marrow biopsy/aspirate](#) and [TLS prophylaxis](#).
- b. Protocol therapy may last up to 26 cycles (~ 24 months), until unacceptable toxicity or disease progression (see [Section 5.7](#) for more comprehensive list). If a patient is still benefiting from treatment at the completion of 26 cycles of therapy, we will consider amending the study to extend the duration of therapy for that particular patient.
- c. Each treatment cycle lasts 28 days. The cycle duration does not change, even if venetoclax is held (Note: exceptions due to unusual operational considerations may be permitted; see [Section 6.2](#)).
- d. Cycle 1 Day 1 is defined as the day of venetoclax and romidepsin initiation. Delay the Cycle 1 Day 1 dose if the participant is experiencing laboratory TLS as defined in [Appendix B](#).
- e. Assessments must be **performed and reviewed within 72 hours prior** to the C1D1 venetoclax dose (except [tumor imaging](#)).
- f. Cycle 1 Day 2-7 ( $\pm$  2 hours) laboratory assessments must be performed and reviewed prior to administration of the Cycle 1 Day 2-7 venetoclax doses.
- g. *End of protocol therapy (EOT) assessments* to be performed no later than 7 days after decision to end treatment (except tumor imaging); assessments performed after last dose of study agent and within 7 days of the decision to end treatment may serve as EOT assessments. **NOTE:** Tumor imaging performed after last dose of study agent and within 28 days of the decision to end treatment may serve as EOT imaging assessment.
- h. *Safety visit* to occur 30 (-2/+7) days post-last dose of protocol therapy. Expedited reporting will occur during this period (See [Section 7.7.2](#)). Safety follow-up may be extended until resolution/stabilization of reportable AEs.
- i. For participants yet to progress, Response Follow-up will occur every 2 months (+/- 7 days) from the day of last response evaluation until progression or the initiation of a new therapy.
- j. Participants who end Response Follow-up will enter Survival Follow-up. Survival assessment to occur bi-annually or as requested by the Study PI via medical record review, review of social security registry, or telephone call.
- k. *Informed consent* process to be fully documented (see [Section 16.4](#)). Informed consent must occur prior to any research only (non-SOC) screening procedures.
- l. *Medical history* to include a review of treatment history, any ongoing medical conditions and medical history pertaining to eligibility on study and involvement during study
- m. *Eligibility criteria* are detailed in [Section 3.0](#).
- n. *Registration* into a COH clinical trial management system (CTMS).
- o. *Standard physical exam* includes weight and skin analysis.
- p. *Vital signs*: heart rate, blood pressure, respiration rate, and temperature.
- q. *Concurrent medications* and reason for administration to be documented from within 10 days prior to protocol therapy up to 30-days-post last dose visit. See [Section 5.9](#) for concomitant medication restrictions and guidelines.
- r. *Adverse event (AE)* will be assessed using CTCAE v.5.0. SAEs related to study procedures will be recorded and reported from time of informed consent until Day 1 of protocol therapy.
- s. Toxicities AE recording and reporting will continue until the completion of [Safety Follow-up period](#) or until resolution or stabilization of any reportable AE occurring during Safety Follow-up.
- t. *Women of child bearing potential*: Pregnancy serum or urine test.
- u. *Screening laboratory assessments* to be performed within 14 days prior to start of protocol therapy.
- v. *Serum chemistry* panel to include: glucose, Blood Urea Nitrogen (BUN), creatinine, uric acid, total protein, albumin, magnesium, bicarbonate, calcium, inorganic phosphorous, sodium, potassium, chloride, total CO2, total bilirubin, alkaline phosphatase, ALT, AST, and LDH.
- w. *TLS serum chemistry monitoring post-Day 1, Day 2, Day 3, Day 4, Day 5, Day 6, Day 7 and Day 8 dose* to include potassium, uric acid, phosphorus, calcium, and creatinine. **Monitoring times are:** predose, and post dose 6-8 hours

and 24 (+/- 2) hours. Next dose should not be administered until 24 h blood chemistry values are evaluated. See **Table 5.9.1.**

- x. CT/MRI imaging for PTCL at baseline.
- y. *Disease and response assessment:* Cycle 3 Day 1 (-7 days), then every 2 cycles (-7 days). CT scan may take place within 7 days prior to D1 but not after D1 of the cycle in question.
- z. FDG-PET scan will be performed at screening. Subsequent PET scans will not be needed until the EOT visit or disease progression, whichever comes first.
- aa. *Bone marrow biopsy/aspirate* that was performed within 120 days prior to Day 1 may serve as Screening assessment.
- bb. PTCL response (Lugano criteria). Refer to [Section 11.3](#) for details.
- cc. *TLS prophylaxis* to be initiated prior to protocol therapy within 72 hours as stated in [Table 5.9.1](#). Participants should receive continued TLS prophylaxis as clinically indicated.
- dd. Refer to [Section 5.3](#) for the treatment plan. Refer to [Section 6.2](#) for dose modification/ delay guidelines and [Section 5.9](#) for supportive care guidelines.
- ee. Romidepsin will be administered intravenously on Days 1, 8, and 15 of each cycle. A window is allowed for romidepsin infusion visits (within  $\pm 3$  days of day 1 and within +3 days of days 8 and 15)
- ff. *Pill Diary* will be given to the participant and will be reviewed for adherence. See [Appendix G](#).
- gg. *Baseline tissue:* Archival tissue of a biopsy and if applicable, fresh core or excisional biopsy of a tumor lesion at time of standard of care biopsy.
- hh. *Optional:* Research fresh core or excisional biopsy of the tumor lesion only if the participant is willing.

## **11.0 ENDPOINT EVALUATION CRITERIA/MEASUREMENT OF EFFECT**

---

### **11.1 Safety**

Toxicity will be graded according to the NCI-Common Terminology Criteria for Adverse Events version 5.0. During the first 2 cycles, all grades of toxicity will be collected. After cycle 2, only the highest grade of any toxicity will be collected for each cycle during protocol treatment and for the period of safety follow-up after end of treatment.

### **11.2 Unacceptable Toxicity During Safety Lead-In**

Unacceptable toxicity will be defined as one of the following AEs that is **at least possibly related** to either venetoclax or romidepsin treatment within the first 2 cycles of protocol therapy:

#### *Hematologic*

- Grade 3 or 4 neutropenia lasting > 7 days (despite the use of growth factor support)
- Grade 3 or 4 thrombocytopenia associated with bleeding requiring transfusion
- Grade 4 anemia not associated with lymphoma

#### *Non-hematologic*

- Clinical TLS (per Howard criteria)
- Grade 4 metabolic laboratory abnormalities that do not resolve within 3 days to  $\leq$  Grade 2 with supportive measures
- Any other  $\geq$  Grade 3 toxicity that does not resolve to  $\leq$  Grade 1 or baseline within 7 days with the **exception of**:
  - Grade 3 asymptomatic laboratory abnormalities, including lipase or amylase, that are not clinically relevant, not requiring hospitalization or delay of treatment
  - Grade 3 nausea, vomiting, or fatigue controlled with supportive measures
  - Vitiligo

### **11.3 Efficacy Endpoints**

#### **11.3.1 PTCL Efficacy Endpoints**

Disease parameters and methods for assessing the disease are in [Appendix C-1](#). PTCL response will be assessed using Lugano Classification (see [Appendix C-2](#)) [50]. Endpoints are described in [Table 11.3](#).

**Table 11.3. Clinical Endpoints**

Endpoint	Patients	Definition
Overall response rate (ORR)	Evaluable patients	Proportion of patients achieving CR or PR
Complete response (CR) rate	Evaluable patients	Proportion of patients achieving CR
Time to response	Evaluable patients	Date of initiation of protocol treatment to date when criteria for response (PR or CR) is first met
Duration of response (DOR)	CR and PR only	Date when criteria for response (CR or PR) is first met until date criteria for PD or relapse is first met
Progression free survival (PFS)	Evaluable patients	Date of initiation of protocol treatment to date criteria for PD is first met or death as a result of any cause
Overall survival (OS)	Evaluable patients	Date of initiation of protocol treatment to date of death from any cause

**Note:** Evaluable patients are patients evaluable for response, as defined in [Section 12.3](#).

## 12.0 STATISTICAL CONSIDERATIONS

---

### 12.1 Statistical Design

This is a multi-institution, single arm Phase 2 trial to evaluate the anti-tumor activity and safety/tolerability of venetoclax with romidepsin in patients with relapsed/refractory mature T-cell lymphoma. Patients will take oral venetoclax daily and romidepsin on days 1, 8, and 15 of each cycle for up to 26 cycles (28-day cycle) Response will be assessed after every 2 cycles until disease relapse/progression. Patients will be followed for 24 months after the end of protocol treatment. The primary endpoint is overall response rate. Secondary endpoints include toxicities, CR rate, duration of response, time to response, PFS, and OS. The study will accrue up to 18 evaluable patients for the primary response endpoint evaluation. The first 6 patients enrolled on the study will be part of a Safety Lead-in to evaluate the safety and tolerability of the proposed dose of venetoclax with romidepsin as described below in [Section 12.1.1](#).

#### 12.1.1 Safety Lead-In

Prior to formally initiating the Phase 2 response evaluation, a patient Safety Lead-in will be conducted to ensure the proposed treatment is tolerable. Up to 6 evaluable patients may be enrolled in two cohorts of 3 patients each at the proposed venetoclax dose (maximum dose of 800 mg/day with a 1-week dose ramp up schedule) plus romidepsin as outlined below. Initially up to 3 evaluable patients can be enrolled and treated. After 3 patients are treated and evaluated for unacceptable toxicities, if 0/1 out of 3 evaluable patients experience unacceptable toxicities during the first 2 cycles, up to 3 additional patients will be enrolled and treated to bring the total number of patients treated to 6. If  $\leq 1/6$  evaluable patients experience unacceptable toxicities during the first 2 cycles, the proposed treatment dose/schedule (including ramp-up) will be considered tolerable and be used for the subsequent Phase 2 response evaluation. At any time during the Safety Lead-in, if  $\geq 2$  patients experience unacceptable toxicities during the first 2 cycles, the accrual will be suspended and the study will be amended. The unacceptable toxicities are defined in [Section 11.2](#). Unacceptable toxicities will be evaluated during the first 2 cycles of therapy to ensure monitoring of participants during the venetoclax ramp-up period (Cycle 1) and while participants are on steady-state venetoclax dose (Cycle 2). Patients inevaluable for unacceptable toxicities during the Safety Lead-in will be replaced (see below in [Section 12.3](#)).

#### 12.1.2 Phase 2

The Phase 2 response evaluation will accrue a minimum of 7 evaluable patients and a maximum of 18 evaluable patients. Patients enrolled during the Safety Lead-in period of the study (n=6) will be included in the Phase 2 response evaluation provided that they are evaluable for response (defined in [Section 12.3](#)). The response evaluation will be based on a Simon's Two-Stage Optimal design [53], to distinguish a promising 30% response rate (alternative hypothesis) from a disappointing rate (null hypothesis) of 10%, at a one-sided type I error of 10% and a power of 80%. In the first stage, 7 evaluable subjects will be accrued. If there is 0 response among the 7, the study accrual will be suspended. If there are 1 or more responses among the 7, the study will remain open to accrue a total of 18 evaluable patients. Observing 4 or more responses among 18 evaluable patients will reject the null hypothesis and indicate the response rate being promising in this study setting. Observing 3 or fewer responses among 18 evaluable patients will fail to reject the null hypothesis and will not establish efficacy of the treatment.

For the purpose of the 1st stage response evaluation, study accrual may be temporarily suspended until all Stage 1 enrollments are assessed for response after at least 4 cycles of treatment or are otherwise off-treatment. If by that time no responders have been observed, the study accrual will be terminated. On

the other hand, if at least one responder has been observed prior to enrolling the 7th patient for Phase II, then Phase II accrual will continue directly to Stage 2 without interruption.

If no toxicity is noted at the proposed dose/schedule and there is no efficacy either, the protocol may be amended after discussion with the industry partner to increase the maximum dose of venetoclax up to 1200 mg/day.

### **12.2 Accrual and Expected Duration of Trial**

The expected sample size for the Phase 2 response evaluation is 18 patients evaluable for response (assuming the response evaluation passes the first stage). Patients enrolled during the Safety Lead-in of the romidepsin/venetoclax combination will be included in the Phase 2 response evaluation if they are evaluable for response which requires a response evaluation after 2 cycles. We expect that all patient enrolled during safety lead-in will have a response evaluation after 2 cycles. Therefore, the total sample size for the study including the Safety Lead-in is expected to be 18 evaluable patients. Assuming approximately 10% of the patients need to be replaced for safety lead-in or Phase 2 evaluation, the maximum sample size for evaluating the combination of venetoclax and romidepsin is 20 patients.

The 6 patients enrolled on the previous versions of protocols with single agent venetoclax will be analyzed separately and excluded from the main analyses which evaluate the combination of venetoclax and romidepsin. Therefore, the maximum sample size of the study will be 26 accounting for these 6 prior enrollments.

City of Hope saw ~160 PTCL patients per year, with ~30 new patients per year (mix of newly diagnosed and relapsed or refractory). This will be a multicenter study with 3 total sites. We expect a total accrual of 1-2 patients per month across all sites. Therefore, accrual is expected to be completed in 24 months.

Participant duration is planned for 4 years which includes maximum time for treatment (24 months) and expected post-treatment follow-up (24 months). The estimated total study duration will be 6 years, with 2 years of accrual and approximately 4 years of treatment and follow-up for the last patient.

### **12.3 Evaluable Participants and Participant Replacement**

- ***Evaluable for unacceptable toxicity during Safety Lead-in:*** Patients evaluable for unacceptable toxicity (defined in [Section 11.2](#)) are:
  - 1) Those who received at least 75% of the total dose of each drug for the first 2 cycles of therapy combined OR
  - 2) Those who experience any unacceptable toxicity during the first 2 cycles regardless of actual dose received.

During safety lead-in, patients who are not evaluable for unacceptable toxicities will be replaced.

- ***Evaluable for response:*** Patients evaluable for response are those who received at least 2 cycles of protocol treatment and have a response evaluation after 2 cycles. Subjects who terminate treatment prior to 2 cycles due to disease relapse/progression or unacceptable toxicity will be considered evaluable for response and be considered non-responders. Patients who terminate prior to 2 cycles for other reasons will be inevaluable for response. Patients not evaluable for response will be replaced.

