### Unacceptable toxicity for Safety Lead-in

Unacceptable toxicity will be defined as one of the following AEs that is at least possibly related to either study drug within the **first 2 cycles** of protocol therapy:

- *Hematologic*
  - Grade 3 or 4 neutropenia lasting > 7 days (despite the use of growth factor support)
  - Grade 4 thrombocytopenia associated with bleeding requiring transfusion
  - Grade 4 anemia not associated with lymphoma
- *Non-hematologic*
  - Clinical TLS (per Howard criteria)
  - Grade 4 metabolic laboratory abnormalities that do not resolve within 3 days to ≤ Grade 2 with supportive measures
  - Any other ≥ Grade 3 toxicity that does not resolve to ≤ Grade 1 or baseline within 7 days with the exception of:
  - Grade 3 asymptomatic laboratory abnormalities, including lipase or amylase, that are not clinically relevant, not requiring hospitalization or delay of treatment
  - Grade 3 nausea, vomiting, or fatigue controlled with supportive measures
  - Vitiligo

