#### **5.6 Duration of Therapy and Criteria for Removal from Protocol Therapy**

Participants will receive protocol therapy until one of the below criteria are met:

- Disease progression
- Completed 26 cycles (~24 months) of protocol therapy
- Participant is deemed intolerant to protocol therapy because of toxicity, despite dose modification/ delay
- General or specific changes in the patient's condition which render the patient unacceptable for further treatment in the judgment of the investigator
- Withdrawal of consent for further protocol therapy (see [Section 16.5](#))

Once participants meet criteria for removal from protocol therapy, the participant should then proceed to End of Treatment assessments. If a patient is still benefiting from treatment at the completion of 26 cycles of therapy, we will consider amending the study to extend the duration of therapy for that particular patient.

Documentation of the reason for discontinuing protocol therapy and the date effective should be made in the source documentation and appropriate eCRF. The COH DCC should be promptly notified of the change in participant status.

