#### **5.7 Follow-Up**

Following completion of protocol therapy, all participants will enter follow-up for up to 24 months after ending protocol treatment. This is comprised of:

- **Follow-up for safety**- All participants will be followed until resolution or stabilization of reportable AEs occurring during protocol therapy or starting within 30-days post last dose of protocol therapy. Refer to [Section 7.7](#) for reporting details.
- **Follow-up for response** for those who have yet to have disease progression.
- **Follow-up for survival** - for those who initiated an anti-cancer therapy or have disease progression.

Assessment time points and windows are detailed in [Section 10.0](#).

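### Table 11.3 restricts PFS and OS to response-evaluable patients, so read literally some early deaths drop out of endpoints that count death from any cause

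*Combined protocol and SAP*

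**What the plan says.** Table 11.3 gives each endpoint a population and a definition. OS runs as "Date of initiation of protocol treatment to date of death from any cause". PFS starts at the same point and ends at progression or death, whatever the cause. The population entry for both is evaluable patients, and the note under the table reads "Evaluable patients are patients evaluable for response, as defined in" Section 12.3.

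Section 12.3 requires at least 2 cycles of treatment and a response evaluation after them. Patients who stop earlier for relapse, progression or unacceptable toxicity are kept as non-responders. For everyone else: "Patients who terminate prior to 2 cycles for other reasons will be inevaluable for response. Patients not evaluable for response will be replaced".

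No other section names a different population. The synopsis endpoint table has no population column, Section 12.1 only lists the secondary endpoints, and Section 12.5 specifies Kaplan-Meier without saying for whom. Section 5.7, however, plans follow-up without regard to evaluability: "all participants will enter follow-up for up to 24 months after ending protocol treatment".

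**The concern.** A response-evaluable set can be defended for a response rate in a small two-stage trial. It does not suit a time-to-event endpoint that starts at first dose and counts every death, because membership is settled by what happens during the following 56 days. A patient who dies on day 30 of an unrelated cause has, by definition, both a PFS event and an OS event. Under the literal rule that patient appears in neither analysis, and a replacement takes the place.

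Dropping such a death removes an event at the start of the curve and biases the estimates upward. Patients who leave alive for other reasons are also lost, although Kaplan-Meier could use their follow-up up to censoring. What is at stake is the accuracy of the reported PFS and OS, not the go/no-go decision.

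**Working it through.** **1. Who is in and who is out, reading Table 11.3 with Section 12.3**

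| Course after first dose | In the PFS/OS set? |
|---|---|
| Stops before 2 cycles for relapse or progression | Yes |
| Stops before 2 cycles for unacceptable toxicity | Yes |
| Dies before 2 cycles, cause attributed neither to lymphoma nor to study drug | No, replaced |
| Leaves alive before 2 cycles for another Section 5.6 reason | No, replaced |
| Completes 2 cycles but has no response evaluation afterwards | No, fails the basic condition |

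Two texts bear on the size of the excluded group.

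- The lead-in definition of unacceptable toxicity is broad on causality: "one of the following AEs that is at least possibly related to either study drug". Many early deaths would therefore stay in. That definition is written for the Safety Lead-in only, and how an early death would be classed in Phase 2 is not stated.
- Section 5.6 allows removal for "General or specific changes in the patient's condition which render the patient unacceptable for further treatment in the judgment of the investigator". Clinical decline without documented progression could be recorded there and so fall under other reasons.

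**2. The plan's own figures**

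- Simon rule (Section 12.1.2: stop if 0 of 7 respond, reject the null with 4 or more of 18). The exact binomial calculation gives type I error 0.0893 at a 10% response rate and power 0.800 at 30%, in agreement with the stated 10% and 80%.
- Maximum for the combination (Section 12.2): 18 / (1 − 0.10) = 20. At most 2 treated patients are thus planned to fall outside the evaluable set.

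**3. Effect of dropped deaths on a survival proportion**

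Let s patients be event-free among 18 analysed, with k early deaths omitted and no other censoring. The reported value is s/18; the value with those deaths counted is s/(18 + k).

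| s | Reported (of 18) | k = 1 (of 19) | k = 2 (of 20) |
|---|---|---|---|
| 6 | 33.3% | 31.6% | 30.0% |
| 9 | 50.0% | 47.4% | 45.0% |
| 12 | 66.7% | 63.2% | 60.0% |

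The shift is about 2 to 7 percentage points. Clopper-Pearson 95% limits are 26.0% to 74.0% for 9/18, 24.4% to 71.1% for 9/19 and 23.1% to 68.5% for 9/20.

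**4. Effect at the end of cycle 2**

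Take 20 treated and 2 replaced. Of the replaced, k died early and 2 − k are alive and followed; d deaths occurred among the 18. Compare (18 − d)/18 with (20 − d − k)/20.

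| | d = 0 | d = 2 | d = 4 |
|---|---|---|---|
| k = 0 | 100% vs 100% | 88.9% vs 90.0% | 77.8% vs 80.0% |
| k = 1 | 100% vs 95.0% | 88.9% vs 85.0% | 77.8% vs 75.0% |
| k = 2 | 100% vs 90.0% | 88.9% vs 80.0% | 77.8% vs 70.0% |

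The overstatement is about 3 to 5 points for one omitted death and 8 to 10 for two. With no omitted death, the evaluable-only figure is 0 to 2 points too low.

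**5. Effect on a median, which Section 12.5 reports**

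Assume exponential survival with median m in the evaluable set, k of 20 dying early, and the rest following the same curve. The all-treated median is then m × log2((20 − k)/10), or 0.926m for k = 1 and 0.848m for k = 2. A 6-month median would be 5.56 or 5.09 months.

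**6. How likely is at least one such death?**

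For an assumed per-patient risk q over 56 days and 20 treated, the chance is 1 − (1 − q)^20: 18% at q = 1%, 33% at 2%, 64% at 5%. The expected number, 20q, is 0.2, 0.4 and 1.0.

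**The case against.** The strongest reply is that the effect is small and hypothetical. Section 12.3 already keeps early stops for progression or unacceptable toxicity and never names death. No document gives a rate for the deaths that remain, and the expected number at the assumed risks is one or fewer. The shift is small beside an interval 48 points wide, and the endpoints are secondary. Early deaths are not hidden either, since Section 14.3.2 requires expedited reporting of all deaths within 30 days of active treatment. All of this stands, and it limits the weight of the point. It does not make the stated population right: sampling error is shown by the interval, whereas this bias is not.

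Two further replies also stand in part.

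- **Direction.** It is not always upward. If both replaced patients were alive and event-free, 9/18 = 50.0% would become 11/20 = 55.0%.
- **Scope.** The excluded group cannot be sized exactly. The Response paragraph of Section 2.7 says treatment is ended for progression only after at least two cycles, while Section 12.3 provides for earlier stops for that reason. Those passages must be reconciled. With the patients who lack an evaluation after 2 cycles, this could widen the group rather than remove it.

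**Conclusion.** The concern holds. As written, the PFS and OS population is selected on events after the start of treatment and, read literally, omits some deaths that the endpoint definitions count. This is a literal reading of two sections together, not an explicit rule about death.

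The likely size is modest: about 2 to 7 points on a mid-curve proportion for one or two omitted deaths, and up to 10 points at the end of cycle 2 if both planned replacements were early deaths. Two is an upper case, because it spends the whole 10% replacement allowance on one cause. The number of such deaths is an assumption throughout. The primary ORR test is not affected. The correction should be made before analysis, when the choice cannot be influenced by results.

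**What to change.** In Table 11.3, change the population for PFS and OS to all patients who received at least one dose of either drug under the combination protocol. The 6 earlier single-agent venetoclax patients stay separate, as Section 12.2 provides.

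In Section 12.5, add the censoring rule:

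- All deaths count as events. Say expressly whether this includes, for PFS, a death after a new therapy, since response follow-up ends there (Table 10.0, note i).
- Patients who leave alive without an event are censored at the last disease assessment for PFS and at last contact for OS.
- A patient with no post-baseline assessment is censored at treatment start for PFS and still contributes to OS.
- Where consent to future data collection is withdrawn (Section 17.5), censor at the last date for which data may be used.

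The data are largely planned already. The first scheduled response assessment is at Cycle 3 Day 1, but an early leaver may have end-of-treatment imaging, since a scan after the last dose and "within 28 days of the decision to end treatment may serve as EOT imaging assessment" (note g). Note j adds: "Participants who end Response Follow-up will enter Survival Follow-up".

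Leave the Section 12.3 definition, the ORR and CR rate populations and the Simon rule unchanged. The cost is two table entries and a short censoring statement, with no loss of power for the primary endpoint (0.800 at a 30% response rate). PFS and OS will look slightly less favourable if the added patients died early, and could move the other way if they did not. Follow-up may be limited for patients who withdraw consent to data collection.
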